10.1 Analysis Populations

The following analysis populations are defined for the different types of data analysis:

• Intention-to-treat (ITT) Population

The ITT Population will include all patients randomized into the study. Treatment classification will be based on the randomized treatment;

• Modified intention-to-treat (mITT) Population

The mITT Population will include patients randomized and received at least 1 dose of any study drug. Treatment classification will be based on the randomized treatment. The mITT population will be used for the primary analysis of all efficacy endpoints;

• Per Protocol (PP) Population

The PP Population will include all patients in the mITT population and who did not experience a major protocol deviation that potentially impacted the primary efficacy endpoint. The PP population, along with the reason for exclusion, will be finalized prior to study end.

Safety Population

The Safety Population will include all patients who receive at least 1 dose of any randomized study drug. Treatment classification will be based on the actual treatment received. The Safety Population will be the primary population used for the safety analyses.

10.2 Efficacy analysis

The primary efficacy analysis will compare the change in 24-hour SBP assessed by ABPM from baseline (Visit 2) to the End of Treatment (Visit 7) between finerenone and spironolactone. Statistical analyses will be primarily descriptive. No formal hypothesis testing will be conducted. Descriptive statistics (eg, mean, standard deviation, median, minimum and maximum) will be presented for continuous variables. Frequencies and percentages will be presented for categorical and ordinal variables.

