1.1 Rationale

It is well recognized that renal epithelial MRs modulate salt and volume handling and BP regulation by the kidney. MRs may also modulate BP through effects on endothelial and vascular function. Reductions in BP load on the vasculature can protect against target organ damage in patients with CKD associated with T2D. Therefore, the impact of MRAs including finerenone on pathways regulating BP load on the vasculature should be considered.

Previous trials have reported conflicting data about the antihypertensive effects of

finerenone. A study by Filippatos et al demonstrated that finerenone can reduce SBP by 3.31 mmHg in 1530 DKD patients with a history of CVD and 3.11 mmHg in 1303 patients without a history of CVD⁹. Bakris et al included 821 patients with diabetes and high or very high albuminuria, suggesting that the mean differences of SBP between the placebo and 7.5-, 10-, 15-, and 20-mg/d finerenone groups are -2.8mmHg, 0.1mmHg, -5.1mmHg and -4.7mmHg⁷. Agarwal et al included 823 patients with type 2 diabetes and CKD who were randomized into a placebo or finerenone group, they found the 10-, 15-, and 20-mg/d finerenone groups exhibit a change in 24-h SBP of -8.3mmHg, -11.2mmHg and -9.9mmHg, respectively¹⁰. They also evaluated the antihypertensive effect of finerenone in resistant hypertension of CKD, the results indicate that finerenone is associated with a lower SBP reduction compared with spironolactone¹¹.

We conducted a randomized pilot study to investigate the antihypertensive efficacy and safety of finerenone versus spironolactone in patients with PA. In this pilot study, a total of 60 patients underwent randomization. The mean change of daytime SBP in the finerenone group was -9.9±13.0 mmHg, which was not significantly different from that in the spironolactone group (-7.8±10.2 mmHg, P=0.49). Changes in daytime DBP (-4.9±7.9 mmHg for finerenone and -5.0±8.4 mmHg for spironolactone, P=0.96), 24-hour SBP (-10.9±12.5 mmHg for finerenone and -7.8±9.5 mmHg for spironolactone, P=0.29),24-hour DBP (-5.9±7.4 mmHg for finerenone and --4.7±6.7 mmHg for spironolactone, P=0.50), office SBP (-17.7±19.7 mmHg for finerenone and -17.1±19.0 mmHg for spironolactone, P=0.90), and office DBP (-9.1±8.3 mmHg for finerenone and -6.8±11.8 mmHg for spironolactone, P=0.40) were similar in the two groups. This study provides information for large-scale clinical studies. Therefore, we are planning a multicenter randomized clinical trial next.

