3.2 Study visit

This study will consist of 2 periods:

- 1. A Screening Period (Screening Visit [Visit 1]) of up to 2 weeks;
- 2. A Treatment Period (Visits 2 to 7) of 12weeks;

Patients will complete at least 7 total visits over a period of approximately 3 months, including 5 Clinic Visits and 2 Telephone Visits. Additional Unscheduled Visits may occur at any time during the study.

Screening Period (Visit 1, Week -2~0)

Patients will provide informed consent at the Screening Visit (Visit 1) and undergo assessment for Inclusion/Exclusion Criteria. All patients will undergo 24-hour ABPM at the first visit.

Patients with a confirmed diagnosis of PA who are willing to participate in the study are into the Screening Period. PA is defined as having a positive result of screening and confirmatory tests^{2,11-14}. Screening positive is defined as plasma aldosterone-to-renin ratio (ARR) \geq 20(pg/ml)/(µIU/ml) or ARR \geq 300 pg/ml)/(ng/ml/hr). Plasma aldosterone concentration (PAC) post captopril challenge test (CCT) \geq 110 pg/ml or PAC post seated saline infusion test (SSIT) \geq 80 pg/ml is considered positive.

[Note: $ARR \ge 10(pg/ml)/(\mu IU/ml)$ or $ARR \ge 150(pg/ml)/(ng/ml/hr)$ can be considered positive if the patients with hypokalemia (serum potassium < 3.5mmol/L) or adrenal nodules (diameter > 1cm)].

For the screening test and the confirmatory tests, antihypertensive medication is withheld or changed according to the guideline. Treatment with diuretics is withheld

for at least 4 weeks^{2,13}. β -blockers, angiotensin-converting enzyme inhibitors, and angiotensin-II receptor blockers are stopped for at least 2 weeks. Only the non-dihydropyridine calcium channel blocker, terazosin, and doxazosin are allowed for uncontrolled hypertension.

Treatment Period (Visits 2 to 7, Week $0\sim12$)

All patients who remain on a stable regimen of antihypertensive treatment, or who are not taking any antihypertensive medications through the Screening Period will be eligible for randomization. Eligible patients will be contacted via Clinic Visits (Visit 2) to be informed about the study qualification and to schedule their treatment period. Eligible patients will be randomized 1:1 into 1 of the 2 treatment groups (Finerenone and spironolactone).

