10.4 Sample Size

The assumption of this study is that the antihypertensive effect of finerenone is non-inferior to spironolactone. The sample size was based on data from our pilot study to assess the efficacy and safety of finerenone versus spironolactone in PA. According to pilot study, the standard deviation of 24-hour SBP were12.5mmHg in the finerenone group and 9.5mmHg in the spironolactone group respectively. Previous studies on antihypertensive RCT mostly set blood pressure in the range of 2-6 mmHg as the non-inferior limit $^{17-19}$, while the European Society of Hypertension pointed out that a difference of less than 5mmHg is clinically acceptable 20 . Therefore, the non-inferior limit is set as 4 mmHg. Using 80% power to measure the antihypertensive effect between the two groups, a unilateral significance level α =0.025, a total sample size of 244, an estimated dropout rate of about 20%, and a final sample size of 244/0.8=306, with a target of 153 patients per group.

11 Data Management and Record Keeping

A Data Safety Monitoring Board (DSMB) will meet periodically to monitor the study. The primary function of this committee is safety monitoring, and the committee will not discontinue the study for a finding of positive efficacy for any of the doses being considered. As part of these reviews, the DSMB will receive summaries of study conduct measures as well as safety and efficacy data. The DSMB may recommend discontinuing enrollment for a dose for safety or lack of efficacy.

The DSMB Chair is an expert in PA who is well-versed in GCP management. The Chair's responsibilities include facilitating discussions, integrating different perspectives, and reaching consensus among the responsible centers. The Chair is also committed to participating in DSMB activities throughout the trial period. The DSMB will hold regular meetings to review the trial's progress and ensure the research's quality. Please see the attachment for the full membership list. The main members include:

Chairman: [name] is an Associate Professor at West China School of Public Health, Sichuan University, Chengdu, Sichuan, People's Republic of China.. Her research focuses on adrenal disorders, particularly primary aldosteronism. She has rich clinical experience in the clinical diagnosis and treatment of adrenal diseases.

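### Section 10.2 describes the primary comparison as descriptive, untested and without baseline adjustment, although the trial is sized for non-inferiority and records a baseline ABPM in every patient

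*Protocol*

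**What the plan says.** Protocol section 10.2 sets out the primary analysis: "The primary efficacy analysis will compare the change in 24-hour SBP assessed by ABPM from baseline". It labels baseline as Visit 2 and takes the final value from Visit 7, with finerenone set against spironolactone. It then adds: "Statistical analyses will be primarily descriptive. No formal hypothesis testing will be conducted". The output it describes is a set of summaries: "Descriptive statistics (eg, mean, standard deviation, median, minimum and maximum) will be presented for continuous variables". No model, estimator, covariate or confidence interval is named. Section 5 of the synopsis says the same, except that it omits the sentence on hypothesis testing.

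Section 10.4 starts from a different premise: "The assumption of this study is that the antihypertensive effect of finerenone is non-inferior to spironolactone". It sets a 4 mmHg margin, a one-sided alpha of 0.025 and 80% power, and arrives at 244 patients, or 306 after allowing for 20% dropout. For variability it states that "the standard deviation of 24-hour SBP were12.5mmHg in the finerenone group"; its figure for spironolactone is 9.5 mmHg. Section 1.1 shows that these are SDs of the change: "24-hour SBP (-10.9±12.5 mmHg for finerenone and -7.8±9.5 mmHg for spironolactone, P=0.29".

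On the baseline measurement, section 3.2 says "All patients will undergo 24-hour ABPM at the first visit". Section 6.2 lists ABPM among the Visit 1 procedures, section 6.3.1 does not list it at Visit 2, and Appendix A marks it at Visits 1 and 7 only.

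**The concern.** A non-inferiority conclusion rests on one confidence limit, so the precision of the estimated difference bears directly on the answer. Section 10.2 describes tabulated summaries of change and no inference, which cannot deliver the conclusion for which 10.4 sizes the trial. The comparison it does describe leaves the baseline recording unused as a covariate. A change score generally remains correlated with its baseline: patients who start higher tend to fall further. If one arm happens to start higher, part of that difference passes into the comparison. If finerenone starts higher, it would look better than it is, and the reverse also holds.

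At stake are a wider interval than the same data could give, an estimate that carries any chance baseline difference, and a model that may be chosen after the data have been seen.

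**Working it through.** **Inputs.** SDs of change 12.5 and 9.5 mmHg (sections 1.1 and 10.4); margin 4 mmHg, one-sided alpha 0.025, power 80%, 244 evaluable (10.4), that is 122 per arm at 1:1 (5.1). The protocol gives neither the correlation r between baseline and Week 12 24-hour SBP nor the ratio k of the Week 12 SD to the baseline SD. Both are assumed below and varied.

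**1. The plan's own figure.** Pooled SD = √((12.5² + 9.5²)/2) = √123.25 = 11.10 mmHg. With a true difference of zero, n per arm = (1.96 + 0.8416)² × 2 × 123.25 / 4² = 120.9, so 121 per arm (242) by the normal approximation. The noncentral t calculation gives 122 per arm, 244 in total, with power 80.0%. For dropout, 244/0.8 = 305, and two equal groups of 153 make 306. The stated size is reproduced, and it is based on the unadjusted change.

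**2. Unadjusted precision.** SE = √((12.5² + 9.5²)/122) = 1.42 mmHg, and the 95% half-width is 1.96 × 1.42 = 2.79 mmHg.

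**3. Adjusted precision with equal SDs (k = 1).** ANCOVA variance = change-score variance × (1 + r)/2. Power = Φ(4/SE − 1.96).

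| r (assumed) | variance factor | SE | fall in SE | 95% half-width | power at 122 per arm |
|---|---|---|---|---|---|
| unadjusted | 1 | 1.42 | – | 2.79 | 80% |
| 0.4 | 0.70 | 1.19 | 16% | 2.33 | 92% |
| 0.5 | 0.75 | 1.23 | 13% | 2.41 | 90% |
| 0.6 | 0.80 | 1.27 | 11% | 2.49 | 88% |
| 0.7 | 0.85 | 1.31 | 8% | 2.57 | 86% |

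For r = 0.4 to 0.7, an unadjusted analysis would need about 244/0.70 = 349 to 244/0.85 = 287 evaluable patients for the same precision. The largest observed difference that still meets the margin rises from 4 − 2.79 = 1.21 mmHg to between 4 − 2.33 = 1.67 and 4 − 2.57 = 1.43 mmHg.

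**4. Unequal SDs.** In units of the baseline variance, the change score has variance 1 + k² − 2rk and ANCOVA has k²(1 − r²). The saving is (1 − rk)², which vanishes as rk approaches 1.

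- k = 1.25, r = 0.6: 1.0625 against 1.0000, ratio 0.941. SE falls 3%, to 1.38; power 83%.
- k = 1.3, r = 0.7: 0.8700 against 0.8619, ratio 0.991. SE falls 0.5%, to 1.41; power 81%.

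**5. Chance imbalance (k = 1).** A 1 mmHg baseline difference moves the change-score difference by (1 − r) mmHg. An imbalance of one standard error moves it by 1.42 × √((1 − r)/2), which is 0.78 mmHg at r = 0.4 and 0.55 mmHg at r = 0.7, or 19% to 14% of the margin.

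**The case against.** The strongest reply is that 10.2 does not forbid adjustment. Change from baseline defines the endpoint, and an ANCOVA of change analyses that same endpoint. The sentence on means and SDs is a general rule for tables. Models and covariates are commonly left to an analysis plan, and this trial's plan is not at hand. All of this stands: a missing covariate would not by itself be an error in a protocol. But 10.2 goes further than silence. It calls the analysis descriptive and excludes formal testing, so an analysis plan with an adjusted non-inferiority comparison would have to depart from it.

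A reader might infer that the unadjusted result would be biased or the trial underpowered. The documents do not support that. Under randomisation the change difference is unbiased on average, and 244 gives 80% power without adjustment. Imbalance affects the particular trial obtained, not the long-run validity of the method.

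A reader might also take the 8% to 16% gain as established. It is not, because it rests on an assumed r and on equal SDs. Taken at face value, the pilot SDs of 12.5 and 9.5 sit badly with that: arms that share a baseline SD cannot both have k = 1 and the same r. Entry within an office blood pressure band and response-guided titration also make a larger spread at Week 12 plausible, which would shrink the gain.

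Finally, centre adjustment has no stated basis, since sections 5.1 and 5.2 describe no stratification.

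**Conclusion.** The point holds as a worthwhile improvement, not as a flaw that invalidates the trial. The analysis described in 10.2 does not match the non-inferiority purpose in 10.4 and names no use of the baseline recording as a covariate. In a large 1:1 trial, baseline adjustment is at least as precise as the raw change comparison and removes the linear effect of chance baseline imbalance. The gain runs from about 16% to 8% of the standard error (equal SDs, r = 0.4 to 0.7) down to about 0.5% (k = 1.3, r = 0.7). All of these values of r and k are assumptions.

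Two defects in the same section need no assumption. The no-testing sentence conflicts with a trial sized on a one-sided 0.025 criterion. The baseline label points to Visit 2, where no ABPM is scheduled.

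**What to change.** In section 10.2, and in section 5 of the synopsis where it repeats the text:

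1. State that the primary analysis is an ANCOVA of the change in 24-hour SBP on treatment and baseline 24-hour SBP. Report the adjusted difference, finerenone minus spironolactone, with a two-sided 95% confidence interval. Non-inferiority is concluded if the upper limit lies below 4 mmHg.
2. Delete the sentence excluding hypothesis testing, or reconcile it with 10.4. Keep the descriptive tables as supporting output.
3. Identify baseline as the Visit 1 ABPM instead of Visit 2.

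Centre as a further covariate is optional. The sample size can stay as it is, since any gain from adjustment adds to the planned power. The cost is protocol wording, with no new measurements or patients. The change should be made before outcome data are seen, so that the covariate is fixed in advance.

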The ITT Population will include all patients randomized into the study. Treatment classification will be based on the randomized treatment;

• Modified intention-to-treat (mITT) Population

The mITT Population will include patients randomized and received at least 1 dose of the study drug. Treatment classification will be based on the randomized treatment. The mITT population will be used for the primary analysis of all efficacy endpoints;

• Per Protocol (PP) Population

The PP Population will include all patients in the mITT population and who did not

experience a major protocol deviation that potentially impacted the primary efficacy endpoint. The PP population, along with the reason for exclusion, will be finalized prior to study end.

• Safety Population;

The Safety Population will include all patients who receive at least 1 dose of any randomized study drug. Treatment classification will be based on the actual treatment received. The Safety Population will be the primary population used for the safety analyses.

Efficacy analysis

The primary efficacy analysis will compare the change in 24-hour SBP assessed by ABPM from baseline (Visit 2) to the End of Treatment (Visit 7) between finerenone and spironolactone. Statistical analyses will be primarily descriptive. Descriptive statistics (eg, mean, standard deviation, median, minimum and maximum) will be presented for continuous variables. Frequencies and percentages will be presented for categorical and ordinal variables.

Safety analysis

The safety will be assessed from the time of informed consent until the end of the Follow-up Period. The Safety Population will be the primary population for the safety analysis. All safety endpoints will be summarized descriptively.

Table of Contents

S	ynopsis	. 2
	Title:	. 2
	1.Objectives:	. 2
	2. Efficacy Endpoints:	. 2
	3.Population:	. 3
	3.Study Design and Duration	. 5
	4. Dosage and Route of Administration:	. 7
	5. Statistical Analyses:	. 7
T	able of Contents	. 9
L	ist of Abbreviations and Definition of Terms	11
1.	Introduction	13
	1.1 Rationale	13
	1.2 Risk/Benefit	14
2.	Study Objectives	15
	2.1 The Primary Objective	15
	2.2 The Secondary Objective	15
3	Study Description	15
	3.1 Summary of Study Design	15
	3.2 Study visit	16
4	Selection and Withdrawal of Patients	18
	4.1 Inclusion Criteria	18
	4.2 Exclusion Criteria	18
	4.3 Withdrawal Criteria	19
	4.4 Early Termination Procedures	20
	4.5 Criteria for Temporary Suspension of Dosing	20
5	Study Treatments	21

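### The trial is sized as a formal non-inferiority test with a 4 mmHg margin, but Protocol section 10.2 rules out any formal test

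*Protocol*

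**What the plan says.** Protocol section 10.4 gives the design hypothesis: "The assumption of this study is that the antihypertensive effect of finerenone is non-inferior to spironolactone". After citing earlier trials and a European society's view, it adds: "Therefore, the non-inferior limit is set as 4 mmHg". The calculation is introduced as "Using 80% power to measure the antihypertensive effect between the two groups, a unilateral significance level" of 0.025, and leads to 244 patients, raised to 306 (153 per group) for about 20% dropout.

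Section 10.2 says that the primary analysis compares the change in 24-hour SBP between the arms, and continues: "Statistical analyses will be primarily descriptive. No formal hypothesis testing will be conducted". What follows lists summary statistics only.

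The efficacy paragraph in the synopsis (Statistical Analyses) also calls the analyses primarily descriptive but lacks the sentence that excludes testing. Section 10.1 names the analysis set: "The mITT population will be used for the primary analysis of all efficacy endpoints". The objectives (section 2.1) and the primary endpoint (section 7.1) do not mention non-inferiority.

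**The concern.** A margin, a one-sided alpha and a power belong to a decision rule. Section 10.2 says that no such decision will be made, and its wording covers the primary endpoint, which opens the same paragraph.

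An analyst who follows section 10.2 reports means and SDs by arm and never uses the 4 mmHg margin; 306 patients will then have been recruited for a question that the plan declines to answer. An analyst who follows section 10.4 tests non-inferiority, and a reader can then point to section 10.2 and call the test unplanned. A 95% CI could be computed from the arm summaries in either case, but the protocol does not say that it decides anything.

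**Working it through.** **Inputs**
- SD of change in 24-hour SBP: 12.5 mmHg (finerenone) and 9.5 mmHg (spironolactone), from the pilot study (sections 1.1 and 10.4).
- Margin 4 mmHg, one-sided alpha 0.025, power 80%, dropout about 20% (section 10.4).
- Allocation 1:1 (section 5.2).
- True difference: not stated. Zero is assumed, and it reproduces the plan's number.

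**Step 1. Reproduce the plan's sample size as a non-inferiority test**

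Sum of variances: 12.5² + 9.5² = 156.25 + 90.25 = 246.5.

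Normal approximation: n per arm = (1.960 + 0.8416)² × 246.5 / 4² = 120.9, so 121 per arm, or 242 in total.

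Noncentral t: 121 per arm gives 79.7% power and 122 per arm gives 80.04%. So 122 per arm are needed, or 244 in total, which is the protocol's figure.

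Dropout: 122 / 0.8 = 152.5, rounded up to 153 per arm, or 306 in total. (244 / 0.8 is 305; the extra patient comes from rounding up within each arm.)

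The size of the trial therefore follows from the kind of test that section 10.2 excludes.

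**Step 2. What the sized test would decide**

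The rule that matches one-sided alpha 0.025 is: conclude non-inferiority if the upper limit of the two-sided 95% CI for finerenone minus spironolactone is below +4 mmHg.

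| Per arm | SE = √(246.5/n) | 95% CI half-width (t × SE) | Observed difference must be below | Power at true difference 0 |
|---|---|---|---|---|
| 122 | 1.42 | 2.80 | 4 − 2.80 = +1.20 mmHg | 80.0% |
| 153 | 1.27 | 2.50 | 4 − 2.50 = +1.50 mmHg | 88.1% |

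The second row applies if every randomized patient is analysed.

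**Step 3. Dependence on the assumed true difference**

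At 122 per arm, power is about 56% if the true difference is +1 mmHg, 80% at 0, and above 99% at the pilot's observed difference of −10.9 − (−7.8) = −3.1 mmHg. These figures describe the test; the contradiction does not depend on them.

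**Step 4. The baseline value that the rule needs**

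The synopsis and section 10.2 both place baseline at Visit 2. The Visit 2 procedures in section 6.3.1 include no ABPM, and Appendix A schedules ABPM only at Visits 1 and 7. Section 3.2 agrees: "All patients will undergo 24-hour ABPM at the first visit". The only pre-treatment 24-hour SBP is therefore the one from Visit 1.

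**The case against.** The strongest reply is that the exact criterion, including the model and the CI method, is commonly left to an SAP, and that SAP is not at hand. Section 10.4 already fixes the hypothesis, margin, alpha and sidedness, section 7.1 the endpoint and section 10.1 the population, so the usual confidence-limit rule is implied. An SAP that tested non-inferiority would be carrying out section 10.4. The synopsis merely omits a sentence, and calling analyses primarily descriptive does not by itself exclude one primary test.

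Much of this is fair. An unstated rule alone would be a weak point, the fixed margin and alpha narrow the room for later choice, and the synopsis difference is minor. None of it disposes of the no-testing sentence, which is explicit and unqualified. An SAP can fill a gap in the protocol; it cannot carry out section 10.4 without departing from section 10.2.

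Two further objections bear on the remedy. Simply deleting the sentence would leave the 11 secondary endpoints of section 7.2 without a bar on testing, so limiting it to those endpoints is an acceptable alternative. A per-protocol check is also a usual companion in a non-inferiority trial; the rule below keeps the protocol's choice of mITT as primary and does not prevent one.

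**Conclusion.** The concern holds and must be fixed. Sections 10.2 and 10.4 contradict each other on whether the primary endpoint is tested, and no other section resolves it. The stated margin, alpha and power are attached to no planned test or confidence-limit rule.

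The sample size is sound for the test in section 10.4: 122 evaluable per arm give 80.0% power, given the pilot SDs and a true difference of zero, which the protocol does not state. The fault lies in the analysis text.

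**What to change.** Amend the efficacy paragraphs of the synopsis and of section 10.2 so that they say the same thing:

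1. Delete the no-testing sentence in section 10.2, or limit it to endpoints other than the primary one.
2. In both places, say that analyses are primarily descriptive apart from the primary endpoint.
3. State the rule in both places. The null hypothesis is a mean difference in change in 24-hour SBP, finerenone minus spironolactone, of at least +4 mmHg. Non-inferiority is concluded if the upper limit of the two-sided 95% CI is below +4 mmHg in the mITT population.
4. In the same sentences, take baseline 24-hour SBP from the Visit 1 ABPM instead of Visit 2.

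Optionally, adjust for that baseline value. With equal variances and an assumed baseline to week-12 correlation ρ, the variance is multiplied by (1 + ρ)/2. Power at 122 per arm and a true difference of zero is then 86.0%, 89.9% and 93.5% for ρ of 0.7, 0.5 and 0.3. The contradiction is resolved without it.

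The cost is a protocol amendment to the wording of two paragraphs. The sample size stays at 306, and no further patients or data are needed. Naming non-inferiority in the primary objective at the same time would be helpful but is not essential.
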